4.3 Blinding

This was a phase II open-label study of approximately 179 subjects including healthy controls and subjects at risk for tau accumulation as defined by the sites’ companion protocols. No blinding to flortaucipir treatment was required since all study participants received a single IV bolus injection of ~240 or 370 MBq (6.49 or 10 mCi) of flortaucipir (¹⁸F).

4.4 Determination of Sample Size

No power or sample size calculation was done for this study as there was no hypothesis for testing per study objectives. Approximately 179 subjects including healthy controls and subjects at risk for tau accumulation as defined by the sites' companion protocols were dosed with flortaucipir and underwent a PET scan.

5 CHANGES IN THE CONDUCT OF THE STUDY OR PLANNED ANALYSES

5.1 Changes in the Conduct of the Study

There were no changes in the conduct of the study at the time of preparing this SAP.

6 BASELINE, EFFICACY AND SAFETY EVALUATIONS

6.1 Schedule of Evaluations

Table 3: Schedule of Evaluations

Evaluations	Screen	Pre-dose	Dose	PET Imaging	End of Imaging	2 – 3 days post injection
Signed Consent	X					
Medical / Disease History	X					
Concomitant Meds	X	X				
ECG	X					
MMSE	X					
Physician Visit	X	X				X
OSU TBI-ID	X					
Vital Signs ²		X				X
Pregnancy Test	X	X				
¹⁸ F-AV-1451 Administration			X			
PET Imaging ¹				Continuous 20 minute scan		
Follow-up Phone Call						X
Adverse Event Assessment	X	X	X	X	X	X

¹Sites may elect to perform additional imaging time points with prior sponsor approval.

²Height and weight will be measured prior to injection on imaging day.

6.2 Time Point Algorithms

6.2.5 Windows

For all analyses, results will be summarized at the planned study visit they were obtained.

6.3 Screening and Baseline Assessments

Screening assessments may take place over several days, preferably within 30 days prior to the flortaucipir PET scan, and will include collection of demographics, a medical assessment for eligibility, ECG, a brief cognitive assessment, and a traumatic brain injury questionnaire.

6.4 Efficacy Variables

6.4.1 Primary Efficacy Variable

6.4.1.1 Flortaucipir Quantitation

Standard uptake value ratios (SUVr) will be calculated to estimate tau load globally and in individual regions for the flortaucipir images. A target region derived statistically with a Multiblock Barycentric Discriminant Analysis (MUBADA) method will be used for the global measurement.

Voxels of interest determined in the automated anatomical labeling (AAL) atlas masked to exclude white matter and CSF for amygdala, anterior fusiform, posterior fusiform, anterior hippocampus, posterior hippocampus, anterior parahippocampus, posterior parahippocampus, caudate, frontal, parietal, precuneus, temporal, occipital, left frontal, right frontal, left occipital, right occipital, left parietal, right parietal, left putamen, right putamen, left temporal, right temporal will be applied at the individual region level. A selected white matter region derived using a parametric estimated signal reference intensity (PERSI) method will be used as reference region for all SUVr calculations.

MUBADA SUVr will be the variable used in in the primary efficacy analysis.

6.4.2 Additional Variables

6.4.2.1 Mini-Mental State Examination (MMSE)

The MMSE (Folstein et al., 1975) is a brief instrument used to assess cognitive function in elderly patients. The range for the total MMSE score is 0 to 30, the sum of each correct answer, with higher scores indicating better cognition. The score on a continuous scale will be used for primary objective analysis.

6.4.2.2 Ohio State University Traumatic Brain Injury Identification Method (OSU TBI-ID)

The OSU TBI-ID (Corrigan and Bogner, 2007) short version was used to screen for a history of traumatic brain injury. It is the briefest version that still provides several summary indices on which the original version was validated. To shorten the instrument, TBIs resulting in loss of consciousness are emphasized over less severe injuries.

6.5 Drug Concentration Measurements and Pharmacokinetic Parameters

6.5.1 Handling of Pharmacokinetic Parameter Outliers

No pharmacokinetic parameters or drug concentration measurements will be collected during this study.

6.6 Safety Assessments

6.6.1 *Extent of Exposure and Compliance to Study Treatment*

During the flortaucipir imaging sessions, all subjects received a single IV bolus administration target dose of 240 (6.49 mCi) or 370 MBq (10 mCi) of flortaucipir injection.

6.6.2 *Adverse Events*

An AE is any undesirable experience occurring to a subject during a clinical trial, whether considered related to the study drug or not. AEs are classed by severity and seriousness.

Treatment-emergent adverse events (TEAE) are any untoward medical occurrences associated with the use of a drug in humans. For the purposes of this study, untoward medical occurrences will be considered associated with the use of flortaucipir, and thus be reported as TEAEs, if they occur within 48 hours after administration of the PET tracer. The end of study for the purpose of AE reporting is defined as 48 hours after the administration of flortaucipir injection.

The investigator's verbatim term of both serious and non-AEs will be mapped to system organ class (SOC) and preferred terms (PT) using the Medical Dictionary for Regulatory Activities (MedDRA) Version 17.1.

Investigators will be instructed to report their assessment of the potential relatedness of each AE to protocol procedure and flortaucipir. The assessment of the relationship of an AE to the administration of the flortaucipir is a clinical decision based on all available information at the time of the completion of the eCRF.

Investigators will also assess the severity of AE. Severity is classified as mild/moderate/severe (increasing severity).

Serious AEs (SAEs) are events that result in one of the following outcomes or constitute one of the following events:

- Death
- Initial or prolonged hospitalization (other than that required by protocol; "social hospitalization" or any hospitalization for non-medical reasons does not constitute an SAE)
- A life-threatening experience (that is, immediate risk of dying)
- Persistent or significant disability/incapacity
- Congenital anomaly/birth defect
- Considered significant by the investigator for any other reason

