7.7.2. Adverse Event Definitions

Adverse Events

An adverse event is any undesirable experience occurring to a subject during a clinical trial, whether or not considered related to the study drug.

For reporting purposes, Avid will distinguish among pre-existing conditions, trial-emergent adverse events and treatment-emergent adverse events.

Pre-existing conditions (i.e., undesirable experiences, signs or symptoms that begin prior to the Screening Visit) will be recorded on the medical history eCRF pages. During the study, site personnel will record any change in the condition(s) and occurrence and nature of any AEs. Signs and symptoms that are believed to be due to the pre-existing condition under study (started prior to dose of study medication) do not have to be recorded in the AEs section of the eCRF, unless there is an increasing in frequency and severity.

Trial-emergent adverse events are undesirable experiences, signs or symptoms that begin, or worsen in intensity or frequency, after the informed consent, and prior to administration of study drug (^{18}F -AV-1451) at the imaging visit. These will be recorded on the adverse event eCRFs.

Treatment-emergent adverse events are undesirable experiences, signs, or symptoms associated with the use of a study drugs. For the purposes of this study an adverse event will be considered associated with the use of ^{18}F -AV-1451 if it begins or worsens in intensity or frequency within 48 hours after the administration of ^{18}F -AV-1451. Adverse experiences that occur after administration of study drug but outside the 48 hour reporting window will not be reported unless the investigator believes they are attributable to the drug.

The end of study for the purpose of adverse event reporting is defined as 48 hours after the administration of ^{18}F -AV-1451 Injection.

Serious Adverse Event (SAE)

A SAE is an AE that results in one of the following outcomes or constitutes one of the following events:

- Death;
- Initial or prolonged inpatient hospitalization (other than that required by protocol; “social hospitalization” or any hospitalization for non-medical reasons does not constitute a SAE);
- A life-threatening experience (that is, immediate risk of dying);
- Persistent or significant disability/incapacity;

- Congenital anomaly/birth defect;
- Considered significant by the investigator for any other reason.

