7.7.3. Adverse Event Documentation

All adverse events must be fully recorded on the adverse event eCRFs. Documentation must be supported by an entry in the subject file. Laboratory tests, vital signs and ECG abnormalities considered by the Investigator to be clinically relevant should be reported on the adverse event eCRFs. Signs and symptoms of each AE should be described in detail (e.g., start and stop dates, severity/intensity, relationship to study drug, action taken, and outcome).

Adverse events and laboratory test abnormalities fulfilling the definition of a serious adverse event should, in addition, be reported on the Serious Adverse Event Reporting Form.

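### Two separate gaps between SAP and protocol affect the adverse event tables: the TEAE definition omits worsening, and events reportable outside the 48-hour window, including serious ones, are listed but not summarized

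*SAP*

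**What the plan says.** **Definition.** Protocol 7.7.2 regards an adverse event as associated with the tracer "if it begins or worsens in intensity or frequency within 48 hours after the administration of" the injection. SAP 6.6.2 keeps the 48 hours but reduces the condition to the verb occur: events are associated with flortaucipir, "and thus be reported as TEAEs, if they occur within 48 hours after administration of the PET tracer".

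**Records with onset before injection.** Protocol 7.7.2 also defines trial-emergent events, those "that begin, or worsen in intensity or frequency, after the informed consent, and prior to administration of study drug". It adds: "These will be recorded on the adverse event eCRFs". The adverse event data will therefore contain records that start before dosing.

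**Dates.** Protocol 7.7.3 gives as examples of what each record should describe "start and stop dates, severity/intensity, relationship to study drug, action taken, and outcome". SAP Table 4 (8.5.2.7) decides treatment emergence from the start date and time, and from the stop date when the start is missing. Neither mentions a date of worsening.

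**Reporting period.** Both documents close adverse event reporting at 48 hours; the protocol's sentence begins "The end of study for the purpose of adverse event reporting is defined as 48 hours after the administration". The protocol makes exceptions. Events outside the window "will not be reported unless the investigator believes they are attributable to the drug" (7.7.2), so attributed ones remain reportable. Protocol 7.7.4 keeps two kinds of serious event reportable: those after 48 hours that the investigator relates to drug or procedure, and those between consent and dosing that a procedure may have caused.

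**Output.** Protocol 8.2.2 commits to a summary of all patients who have a serious event or who discontinue because of an adverse event. It also provides for presentation by severity, relationship and seriousness. None of this is limited to treatment-emergent events. SAP 8.5.2 to 8.5.2.6 tabulate treatment-emergent events only, and 8.5.2 covers everything else by a listing.

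**The concern.** There are two problems with different causes, and they touch different events.

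The first is one of classification. A SAP programmer who works from 6.6.2 and Table 4 has a start date and no rule for worsening. An event that began before injection and became worse after it is one the protocol's definition was written to catch, and it can drop out of the treatment-emergent tables.

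The second is one of output. The protocol asks sites to report certain serious and drug-attributed events outside the window, and it promises to summarize all patients with serious events. The SAP has no table in which those events can appear.

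Expanding the safety database is one of the two primary objectives (Protocol 2, SAP 3). A reader of the safety tables would expect them to show every subject with a reported serious event, or at least to say where the others are.

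**Working it through.** No figure in the plan bears on this point, so the check compares the texts and counts sections.

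1. **How each type of event is handled, assuming complete dates and times:**

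| Event | TEAE, Protocol 7.7.2 | TEAE, SAP 6.6.2 | SAP output |
|---|---|---|---|
| Begins within 48 h of injection | Yes | Yes | Tables |
| Begins between consent and injection, worsens within 48 h, worsening entered as a new dated record | Yes | Yes | Tables |
| Same event, kept under its first start date | Yes | Can be classed No | Listing |
| SAE at, say, 60 h, related to drug or procedure (reportable, Protocol 7.7.4) | No | No | Listing |
| Pre-dose SAE possibly caused by a procedure (reportable, Protocol 7.7.4) | No | No | Listing |
| Non-serious AE at, say, 60 h, attributed to the drug (reportable, Protocol 7.7.2) | No | No | Listing |

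   Row 3 is the first gap: the two definitions disagree. Rows 4 to 6 are the second: the definitions agree, and the conflict is with Protocol 8.2.2.

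2. **Which row applies to a worsening.** The documents do not say whether a site opens a new record or updates the old one. Protocol 7.7.2 does say that "site personnel will record any change in the condition(s) and occurrence and nature of any AEs", but that sentence follows the text on pre-existing conditions held on the medical history pages. It does not settle how a worsening trial-emergent event is entered.

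3. **Count of tables.** The adverse event table sections are SAP 8.5.2, 8.5.2.1 (severity), 8.5.2.2 (relationship to flortaucipir), 8.5.2.3 (relationship to procedure), 8.5.2.4 (serious), 8.5.2.5 (discontinuation) and 8.5.2.6 (death). That is 7, and 7 of 7 are restricted to TEAEs. Section 8.5.2.7 is an imputation rule.

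4. **Exception.** Table 4 can set TEAE = Y for some events that in truth lie outside the window, for example when the start day is missing and the month and year match the injection. Such records would reach the tables.

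5. **Can late events come to light?** The follow-up call is made at 2 to 3 business days and not before 48 h. Ignoring holidays, the earliest is 2 × 24 = 48 h. The latest, with a weekend between, is (3 + 2) × 24 = 120 h. The call therefore falls at or after the end of the window and can reveal such events.

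6. **Weight of one subject.** SAP 4.4 gives about 179 dosed. One subject reclassified under the first gap adds at most 1/179 = 0.0056, or 0.56 percentage points, to a TEAE cell. This is the size of one subject and does not estimate a rate. It does not apply to the second gap, where no TEAE cell changes.

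**The case against.** On the definition, SAP Section 2 says the SAP is to be read with the protocol, so the word occur can be given the protocol's meaning. For the pre-existing condition under study, the protocol calls for an adverse event entry only when it gets worse, which suggests that the record would carry the date of worsening. Both points narrow the first gap to trial-emergent events updated under their old start date. They do not close it, because Table 4 works from start and stop dates and has no step for worsening.

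On the tables, the two documents share the 48-hour window, so late attributed events are not TEAEs in the protocol either. Protocol 8.1 leaves further analysis detail to the SAP, and every adverse event is listed. All of this is true. But Protocol 8.1 already requires listings of all eCRF data, so the summary in 8.2.2 is a separate commitment. Narrowing all patients with serious events to those with serious TEAEs removes content instead of adding detail. The SAP's disposition table (8.2) will give reasons for discontinuation, which answers the discontinuation part only in part: it covers dosed subjects who did not complete the 48-hour follow-up.

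Protocol 8.2.2 could also be read to require tables of non-serious trial-emergent events, which likewise reach only the listing. The point does not go that far. Limiting the general tables to TEAEs is an ordinary choice; the explicit promise about all patients concerns serious events and discontinuations. The case for tabulating late non-serious events attributed to the drug is softer, since the protocol there speaks only of presenting events by relationship.

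A reader might infer that the missing worsening condition is what sends late serious events to the listing. It is not: restoring it would leave rows 4 to 6 of the comparison as they are.

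**Conclusion.** Both inconsistencies stand, as separate points. The first is conditional on site recording practice: if each worsening was entered as a new dated record, it has no effect. The second follows directly from the text: a dated, related SAE at 60 h must be reported under Protocol 7.7.4 and would be absent from every adverse event table.

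The size is unknown. The documents do not give the number of affected subjects, and it may be zero. Three stronger readings are not supported:

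- A reader might infer that safety data are lost or that the 48-hour rates are wrong. The late and pre-dose events are listed, and their absence leaves the TEAE rates right for their window. Only the first gap could change a TEAE count.
- A reader might infer that a zero cell should read 1 (0.6%) for a late SAE. The existing tables are defined by the window and would not change, and events outside it are reported selectively, so a percentage would mislead.
- A reader might infer that any late related SAE is missing from the death table. That holds only if it was fatal.

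**What to change.** **Definition.** In SAP 6.6.2, use the protocol's condition, so that an event counts "if it begins or worsens in intensity or frequency within 48 hours after the administration of" flortaucipir. Classify a worsening by its own date and time. Where that date was not captured, raise a query; if it stays missing, set TEAE = Y, in line with the conservative approach stated in SAP 8.5.2.7.

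**Output.** Keep the 48-hour TEAE tables. Add one summary on the safety population, regardless of treatment emergence, of the number of subjects with:

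- any reported SAE, with fatal ones identified and pre-dose ones shown separately;
- any adverse event leading to discontinuation;
- any adverse event judged related to flortaucipir.

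Give counts without percentages. Add a footnote that events outside the window are reported selectively: SAEs only if judged related to drug or procedure after 48 hours, or possibly caused by a procedure before dosing; other events after 48 hours only if attributed to the drug. A pre-dose SAE in a subject who was never dosed lies outside the safety population in both documents and stays in the listing.

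**Cost.** A change of wording, one extra table and possibly some date queries. The reported event count may rise slightly, and the new table cannot be read as a rate.

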7 STATISTICAL METHODS

7.1 Definitions and Conventions

7.1.1 Analysis Programming Platform

All analysis will be performed using SAS version 9.2 or higher.

7.1.2 Reporting Conventions

Data will be summarized using descriptive statistics (number of subjects [n], mean, standard deviation [SD], median, minimum [min], and maximum [max]) for continuous variables and using frequency count and percentage for discrete variables. Percentages will be rounded to one decimal place, except 100% will be displayed without any decimal places and percentages will not be displayed for zero counts.

The tables and listings will be numbered using a decimal system to reflect main levels of unique tables and listings and sub-levels of replicate tables and listings with maximum two digits per level (e.g., Table XX.YY.ZZ...). Tables will be numbered as 14.YY.ZZ. Baseline analysis will be reported in table series 14.1, efficacy analysis in series 14.2, and safety analysis in series 14.3. Listings will be numbered as 16.YY.ZZ.

7.1.3 Type I Error

Unless otherwise specified, hypothesis testing will be two-sided with type I error rate of 0.05.

7.1.4 Definition of Baseline

Baseline summaries will include all available data from the screening time point (i.e. MMSE, OSU TBI-ID, family and neurologic disease histories, etc.). For the purposes of safety analysis involving change calculations (e.g. vital signs), baseline will be defined as the measurement immediately prior to flortaucipir injection. All efficacy variables to be tested will be based on the initial imaging visit.

7.1.5 Age Calculation

Subjects' ages (in years) will be calculated as the difference between their year of birth and their year of informed consent into the study.

7.2 Handling of Dropouts or Missing Data

Dropout subjects will not be replaced in this study. For situations with no rules for handling missing data the default will be no imputation.

7.3 Interim Analyses and Data Monitoring

No interim analysis or data monitoring is planned for this study.

7.4 Multi-center Studies and Pooling of Centers

This is a multi-center study. Data from all sites will be pooled for the analysis outlined in this SAP.

7.5 Multiple Comparisons/Multiplicity

No multiple comparisons/multiplicity adjustment is planned.

7.6 Examination of Subgroups

No subgroup analysis will be conducted for this study.

8 STATISTICAL ANALYSIS

8.1 Analysis Populations

8.1.1 Enrolled Population

The enrolled population will consist of all subjects who have signed the consent form and for whom data exists in the electronic data capture. The enrolled population will not include screen failures. Disposition will be summarized using the enrolled population.

8.1.2 Safety Population

The safety population will consist of all subjects who received at least one injection of flortaucipir. All baseline and safety data will be summarized using the safety population.

8.1.3 Efficacy Population

The efficacy population will include all subjects with a valid quantitated PET image (available SUVr). All efficacy endpoints will be summarized using the efficacy population.

8.2 Disposition and Withdraws

The enrolled population will be represented in the disposition table. The disposition table will summarize the analysis populations in section 8.1, as well as completed and discontinued subjects.

Discontinued subjects will be defined as any safety subject who fail to complete the 48-hour safety follow-up. Termination status (i.e. 'Completed' and 'Discontinued') and reasons for discontinuation percentages will be based on the safety population. Screen failures will not be included in the summary of disposition.

8.3 Baseline Subject Data

8.3.1 Demographic and Other Baseline Characteristics

All baseline summaries will be based on the safety population. Age (years), gender, race, ethnicity, education, and MMSE will all be summarized in a table and presented in a listing.

8.3.2 Medical and Surgical History

Medical and surgical histories were coded using MedDRA version 17.1 and will be presented in a listing for the safety population.

8.3.3 Concomitant Therapy

Concomitant therapies were coded using WHODRUG Sep 2014 and will be presented in a listing for the safety population.

8.3.4 Neurologic Disease History

Neurologic disease information captured on the case report form (CRF) will be presented in a listing for the safety population.

